	
Examiner
 
- [name]^{1,2}- [name], Drs.^{1,2}- [name], MSc¹- [name] 
¹ University of Applied Sciences and Arts Southern Switzerland SUPSI, Department of Business Economics, Health and Social Care, Physiotherapy Graubünden, [name]
 
² THIM University of Applied Sciences in Physiotherapy, [name]
 
³ Medical Center Bad Ragaz, [name]

Investigator(s):	
Contact / Director of Studies
 
[name], PhD
 
University of Applied Sciences and Arts Southern Switzerland (SUPSI) Department of Business Economics, Health and Social Care Physiotherapy Graubünden [name] [contact] [contact]

Study Centre(s):	Single Centre Study: Rehabilitation Research Laboratory University of Applied Sciences and Arts Southern Switzerland SUPSI Department of Business Economics, Health and Social Care Physiotherapy Graubünden [name]
Statistical Considerations:	
Patellar displacement during mobilization application by the patello. Repeated measures analysis of variance (MANOVA)
 
A 2-factor analysis is carried out.
 
Factor 1: Intervention Patello
 
Factor 2: Time intervention: Start (pre-intervention, 1st measurement), after a single mobilization (2nd measurement), after 10 (3rd measurement), after 20 (4th measurement), after 30 (5th measurement), after 50 mobilizations (6th measurement).
 
The significance level is set at $P < 0.05$, and distatistical data analysis is carried out using the Statistical Package for Social Sciences (SPSS V. 24) from IBM, New York, USA.

SUPSI

GCP Statement:	This study will be conducted in compliance with the protocol presented here, the current version of the Declaration of Helsinki, the ICH-GCP, ISO EN 14155 (where applicable), and the Swiss Human Research Ordinance HFV.
-----------------------	--

SUPSI

Overview of the study

Knee joint mobility can be limited by arthritic or post-operative functional or structural changes. Reduced knee joint mobility can interfere with the affected person's everyday activities. Active movement of the knee promotes the formation of synovial fluid, which is essential for the supply of cartilage tissue. Passive mobilization techniques as part of a physiotherapeutic treatment release structural blockages and favor the fiber alignment of the collagen tissue.

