In order to provide a further passive mobilisation option of the knee joint, specifically Art. Patellofemoral device, independent of therapists, the Patello device was developed. It performs apparatus, passively and continuously mobilization of the patella in the caudal and cranial directions. The movement deflections are determined by the patient independently based on the current tolerability.

Aim of the study

The aim of this study is to determine the effectiveness of the Patello device. We want to prove that the Patello device moves the patella on the patellofemoral bearing.

The primary outcome is the objectification of the displacement of the patella measured with an imaging ultrasound device (esaote MyLabClassicC, Genoa, Italy, www.esaote.com).

As a secondary outcome, the subjective well-being of the subject is recorded, measured using a visual analogue scale (VAS scale 0 - 10).

In order to record a possible positive effect of repetitive mobilization, the measurements are carried out several times: after the positioning of the device (1st measurement, pre-mobilization), after 1 mobilization, after 10 mobilizations, after 20 mobilizations, after 30 mobilizations and after 50 mobilizations (2nd to 6th measurement). The measurements are carried out on 2 days, with a 2-day break in between.

Abbreviations

CEC	Competent Ethics Committee
GCP	Good Clinical Practice
KlinV	Ordinance on Clinical Trials in Human Research Study Schedule

The completion of the measurement series is planned for December 2018, and the completion of the entire project for December 2019.

Table 1: Schedule

June, 2018	July-December, 2018	January-May, 2019	June-December, 2019
Subject Information, Screening, Planning	Data collection and Statistics	Writing the article	Publishing the article

SUPSI

SUPSI

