3.5 Medical product: method of application in the study

As part of this clinical study, the displacement of the patella in the caudal / cranial direction by the Patello device will be recorded and quantified. This is to prove the effectiveness of this device. For more detailed specifications, see Chapter 3.2 Medical Device and Indication.

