4.3 Secondary Objectives

Multiple measurements will be performed to detect a possible sustained and/or cumulative effect of patellar mobilization. The measurements are repeated 2x per week in the same week, with a break of at least 2 days, as described in chapter 4.2.

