9.2.3 Sequence of the measurements

After determining the contact pressure, the pre-mobilization measurement is carried out (**1st measurement**). The ultrasound probe is used to visualize a reference point on the patella and at the same time the lateral femoral epicondyle on the thigh and save it as an image. Afterwards, the mobilization pressure is built up individually up to the tolerance limit of the test subject so that a displacement of the patella caudally takes place. The maximum deflection of the patella to the reference point on the thigh is determined, the device settings are noted and transferred to the data sheet (**2nd measurement**).

As described above, further measurements are carried out according to the following scheme: after 10 mobilisations (**3rd measurement**), after 20 mobilisations (**4th measurement**), after 30 mobilisations (**5th measurement**) and after 50 mobilisations (**6th measurement**).

Table 5: Overview of the course of studies

Time	Preparation	Pre	1 Mob.	10 Mob.	20 Mob.	30 Mob.	50 Mob.
Time (min)		5	10	20	30	40	50
Measurement		1.	2.	3.	4.	5.	6.
Subject information	X						
Consent	X						
Demographics	X						
Intervention			X	X	X	X	X
Ultrasound image		X	X	X	X	X	X
Subj. Well-being		X	X	X	X	X	X

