10 STATISTICAL METHODS

10.1 Hypotheses & Factors

Mobilization of the patella in the caudal / cranial direction by the patello – repetitive mobilizations versus one-time mobilization Objective displacement of the patella:

H0 The patella does not shift significantly more during repetitive mobilizations than during a single mobilization by the patello.

H1 The patella shifts significantly more during repetitive mobilizations than during a single mobilization by the patello.

Subjective well-being of the subject:

H0 Subjective well-being does not change significantly more with repetitive mobilizations than with a single mobilization by the patello.

H1 Subjective well-being changes significantly more with repetitive mobilizations than with a single mobilization by the patello.

A 2-factor analysis is carried out.

Factor 1: Intervention

Factor 2: Time intervention: Start (pre-intervention, 1st measurement), after a single mobilization (2nd measurement), after 10 (3rd measurement), after 20 (4th measurement), after 30 (5th measurement), after 50 mobilizations (6th measurement)

Sample size

The planned sample size is $n = 30$ subjects. This size is expedient, time-wise and financially feasible for the study.

10.2 Criteria for the statistical use of data in the case of incomplete data sets

A complete mobilization interval must be completed for the data to be included in the study. If a mobilisation interval (e.g. interval '20 mobilisations', but termination after 15 mobilisations) has to be interrupted, only the previously collected complete mobilisation interval data can be used. This ensures that all data remains homogeneous and comparable. No substitute is sought for the missing mobilization interval data.

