10.3.2 Primary Analysis

The statistical data analysis is carried out by the statistician after completion of the data collection of the entire project.

Repeated measures analysis of variance (MANOVA) A 2-factor analysis is performed.

Factor 1: Intervention

Factor 2: Time intervention: Start (pre-intervention, 1st measurement), after a single mobilization (2nd measurement), after 10 (3rd measurement), after 20 (4th measurement), after 30 (5th measurement), after 50 mobilizations (6th measurement)

The significance level is set at $P < 0.05$, and the statistical data analysis is carried out with SPSS V. 24.

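### The planned six-level time test does not test the only displacement hypothesis (repetitive versus single mobilisation), and the plan names no contrast or rule that would

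*Combined protocol and SAP*

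**What the plan says.** Section 10.1 states the displacement hypothesis as "H1 The patella shifts significantly more during repetitive mobilizations than during a single mobilization by the patello". The parallel hypothesis for the secondary outcome is "H1 Subjective well-being changes significantly more with repetitive mobilizations than with a single mobilization by the patello". On the measurement schedule, both set measurements 3 to 6 (10, 20, 30 and 50 mobilisations) against measurement 2 (one mobilisation). The pre-mobilisation reading plays no part in either.

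Section 10.3.2, like the synopsis, plans one two-factor repeated-measures (M)ANOVA at a 0.05 level. The first factor is the intervention. The second is "Factor 2: Time intervention: Start (pre-intervention, 1st measurement), after a single mobilization (2nd measurement), after 10 (3rd measurement", continuing to the sixth measurement after 50 mobilisations. Sections 7.3 and 8.1.2 provide no groups and no control, so the first factor has a single level. Section 10.3.3 offers no secondary analysis.

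The overview puts the aim differently: "We want to prove that the Patello device moves the patella on the patellofemoral bearing". Section 3.5 agrees that "the displacement of the patella in the caudal / cranial direction by the Patello device will be recorded and quantified". Section 4.3 adds a secondary objective: "Multiple measurements will be performed to detect a possible sustained and/or cumulative effect of patellar mobilization". For the step between measurements 1 and 2, section 9.2.3 says the pressure is "built up individually up to the tolerance limit of the test subject so that a displacement of the patella caudally takes place".

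**The concern.** With a one-level intervention factor and no contrast, the only test that the plan itself supplies is the overall time effect. It asks whether all six means are equal. The hypothesis asks whether the later readings exceed measurement 2. A shift at the first mobilisation makes the overall test's null false without bearing on the hypothesis. The overall test also has no direction, whereas the hypothesis says more.

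A significant time effect could therefore be reported as a benefit of repetition when the device only moved the patella once and repetition added nothing. Conversely, the aim that the device moves the patella, which needs the pre-mobilisation reading, has no written hypothesis and no test of its own.

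**Working it through.** **The plan's own figure.** The synopsis gives effect size 0.68 and power 0.95 at n = 30. As a two-sided paired t-test at 0.05, the noncentrality is 0.68 × √30 = 3.72 on 29 df, and the power is 0.949. This reproduces the figure. A one-sided paired test gives 0.977. A repeated-measures omnibus test with f = 0.68 gives more than 0.999. The stated power therefore fits a single paired comparison rather than the six-level test, although the documents do not name the test used.

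**Inputs.** From the documents: n = 30, level 0.05, six time levels. Assumed, because the documents give no SD, expected displacement or correlation: one measurement day, compound symmetry, and a first shift s in SDs of the difference between measurements 2 and 1. The hypothesis's null is taken as true, so the means are (0, D, D, D, D, D). The overall time p-value is assumed to decide H1.

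**Overall time test.** With within-subject error SD σ, D = s·σ·√2. The noncentrality is λ = n·D²·(5/6)/σ² = 30 × 2 × s² × 5/6 = 50·s². The multivariate test uses F on 5 and 25 df.

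| First shift s | λ | Rejects |
|---|---|---|
| 0.1 | 0.5 | 6.8% |
| 0.3 | 4.5 | 26.7% |
| 0.5 | 12.5 | 68.2% |
| 0.68 | 23.1 | 93.5% |

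**Direction also required.** Under no gain, the later readings are as likely to lie below measurement 2 as above it, so half of these rejections point the right way: 3.4%, 13.4%, 34.1% and 46.8%. Simulated values are about 4%, 14%, 34% and 48%, the same to within sampling error.

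**Other correlation structures.** Suppose the pre-mobilisation reading correlates less with the loaded readings than they do with each other (0.5 versus 0.8, 0.3 versus 0.9, 0.2 versus 0.95). The multivariate test then rejects in 20%, 18% and 17% of trials at s = 0.3, and in 82%, 76% and 75% at s = 0.68.

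**Contrast picked afterwards.** If any of the four comparisons with measurement 2 may be used without adjustment, at least one is significant in about 14% to 16% of no-gain trials, and at least one shows a significant increase in about 7% to 8%. With Holm adjustment the chance of any rejection is about 4%.

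**A matching contrast.** The mean of measurements 3 to 6 minus measurement 2 rejects in 4.7% to 5.1% of no-gain trials whatever the first shift. Measurement 6 minus 2 also stays close to 5%.

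**The case against.** Nowhere does the plan say that the overall p-value decides H1, and there are signs that it was not meant to. The line introducing section 10.1 names both sides of the comparison, and the power figure fits a paired test. A competent analyst might simply compare later readings with measurement 2. This stands, so the rates above are conditional. It does not supply the missing contrast: which later reading, or what pooling of them, is left open.

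Four stronger readings are tempting, and the documents do not support them.

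- A reader might take every rejection of the overall test as a false claim for H1. Someone who also checks the direction of the means would make about half as many.
- A reader might infer that any contrast chosen after the data are seen inflates the error. Unadjusted picking does; Holm adjustment over the four comparisons keeps it below 5%.
- A reader might infer that section 4.3 demotes the very hypothesis that section 10.1 tests. Section 4.3 goes on to the repeat session in the same week, and section 9.2.4 links lasting or cumulative effects to measuring twice in that week. That is most naturally a between-day objective, and no contradiction with the within-session hypothesis is shown.
- A reader might think that including measurement 1 is itself an error. The aim of showing that the device moves the patella needs that reading; the fault is letting it into the test of a different question.

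**Conclusion.** The point holds and should be settled before analysis. Followed as written, section 10.3.2 gives no valid test of the displacement hypothesis in section 10.1. That conclusion comes from the text and needs no numerical assumption.

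The size is conditional. If the overall time p-value decides H1 and repetition adds nothing, false rejection runs from about 7% at a first shift of 0.1 SD to about 94% at 0.68 SD under compound symmetry, and to about 75% to 82% at 0.68 SD under the other structures tried. With direction required, the compound-symmetry rates are about half. For a very small first shift the excess is minor. The exact rates depend on the assumed shift and correlations; growth with the first shift does not.

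The displacement aim's lack of a hypothesis is a separate gap. The well-being hypothesis lacks a contrast in the same way, but no error rate was worked out for it.

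**What to change.** In section 10.3.2, decide H1 by one contrast that excludes measurement 1. A suitable choice is measurement 6 minus measurement 2 in mm, averaged over the two days within subject, with a paired t-test and a two-sided 95% CI. H1 is supported only if the whole CI lies above zero. Report the other time points against measurement 2 as supportive, with Holm adjustment.

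Add a separate pre-specified test against measurement 1, for example 2 minus 1, for the aim in the overview and section 3.5. State which question is primary or, if both are claimed, the testing order. Use the same repetition contrast, two-sided, for well-being.

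At 0.68 SD of the contrast, the power is 0.949, in line with the synopsis. If 0.68 refers to the one-day SD, averaging two days raises it to 0.986 to 0.999 (between-day correlation 0.5 to 0, assumed). A mixed model on measurements 2 to 6 with subject-level robust errors is an optional way to keep partly completed days. The gain is small: with 20% of subjects stopping early, power was 0.996 against 0.991 for the t-test on complete days under compound symmetry.

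Costs: no new data, but the six-level p-value is no longer the headline result, and a gain confined to the middle intervals could be missed. Section 2.10 requires review by the ethics committee and Swissmedic.

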10.3.3 Secondary Analysis Not

Available.

10.3.4 Interim analyses

The data is processed after the project ends. No additional interim analyses are planned.

10.3.5 Security Analyses

No security analyses are provided.

10.3.6 Discrepancies

Deviations from the planned statistical analysis are recorded and justified and reported to the CEC in the annual report.

10.4 Drop-outs and Missing Data

If a subject wishes to withdraw from the study before the end of all measurement days and interventions, or if he or she has to be excluded by the study leader due to an event, the complete mobilization interval data collected up to that point will be included in the data analysis.

No replacement of test persons is being sought for the missing data sets.

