7.4 Discontinuation of study participation

If a participant withdraws from the study before the measurements have begun, the allocation lot is returned to the pot in a new envelope and a new participant is sought.

If a participant is eliminated during the measurements, all data collected up to that point will be evaluated as far as possible and included in the data analysis (in accordance with Art. 9 ClinO). In this case, no new participant will be recruited to collect the missing records.

The data will be stored encrypted with a code during the study period and evaluation of the data.

The conditions for the termination of the experiment were described in chap. 5.4.

Participants are not disadvantaged by discontinuing their participation in the study.

SUPSI

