8.5 Follow-up treatment of eliminated participants

Data already collected from eliminated participants will be evaluated as far as possible and will be included in the data analysis of the study.

There is no disadvantage for the participants if they discontinue their participation in the study and no further interventions are necessary for follow-up treatment.

If study participation was discontinued due to an excessive reaction/injury occurring during study participation, this will be recorded and reported to the sponsor investigator (head of the research laboratory), who is also the study leader, and the supervisor of the study. If medical care is necessary, the report is forwarded to the business liability insurance of Thim van der Laan AG (Basler Versicherung) in order to ensure the appropriate follow-up treatment.

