9.1.6 Collection of data in case of early termination of studies

For the participants, there is no disadvantage in the event of an (arbitrary) discontinuation of study participation and no further interventions are necessary for follow-up treatment. The data collected to date will be evaluated as far as possible and included in the data analysis (in accordance with Art. 9 ClinO).

If study participation was discontinued due to an excessive reaction/injury occurring during study participation, this will be recorded and reported to the sponsor investigator (head of the research laboratory), who is also the study leader, and the supervisor of the study. In the event of necessary medical treatment, the report is sent to the business liability insurance of Thim van der Laan AG (Basler Versicherung).

The following are recorded:

- Date and time of the incident
- Course of the incident
- Persons involved & witnesses
- Study ID (specified by the CEC)
- Personal data of the person concerned (if not previously recorded)

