10.3 Planned analyses

10.3.1 Datasets and Data Population

Only complete mobilization interval datasets will be included in the study and integrated into the analysis. No new test subject is being sought to replace the missing data.

SUPSI

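### Section 10.4 keeps the completed intervals of a subject who stops, but the only named test in its usual form drops anyone who stops partway through a session (minor)

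*Combined protocol and SAP*

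**What the plan says.** Section numbers are those of the body text, which differ from the table of contents in chapter 10.

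- **Drop-outs, section 10.4.** If a subject withdraws or is excluded, "the complete mobilization interval data collected up to that point will be included in the data analysis". This sentence has no qualifier. Subjects are not replaced.
- **Unit of completeness, section 10.2.** If an interval is interrupted, "only the previously collected complete mobilisation interval data can be used". Completeness is therefore judged interval by interval, and missing intervals are not substituted.
- **Data sets, section 10.3.1.** "Only complete mobilization interval datasets will be included in the study and integrated into the analysis". This is a restriction, again by interval.
- **Discontinuation, sections 7.4, 8.5 and 9.1.6.** These are softer. Section 7.4 has "all data collected up to that point will be evaluated as far as possible and included in the data analysis", 8.5 has "Data already collected from eliminated participants will be evaluated as far as possible", and 9.1.6 has "The data collected to date will be evaluated as far as possible and included in the data analysis". Section 9.4.1 sends stops for side effects to 7.4 and 9.1.6.
- **Analysis, section 10.3.2 and synopsis.** The method begins "Repeated measures analysis of variance (MANOVA". It has two factors, and the time factor has six levels: before mobilisation and after 1, 10, 20, 30 and 50 mobilisations. It is run in SPSS 24 with no procedure named.
- **Other analyses.** The entry is "10.3.3 Secondary Analysis Not", with the word Available on the next line. No mixed model or imputation is described.

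**The concern.** A repeated-measures MANOVA uses each subject's whole vector of measurements, so one missing value removes the subject. A univariate repeated-measures ANOVA run in the usual one-row-per-subject layout does the same, so the ambiguous label does not remove the conflict.

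A subject who stops during the 20-mobilisation interval has three complete measurements. Section 10.4 says they are included, but the named test has no place for them. Either those values leave the test, or the analyst picks an unnamed method once the data are in. Section 10.3.6 allows a justified deviation, but that would be a choice made after data collection.

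Stops within a session are foreseeable. Sections 8.3 and 9.2.3 build the pressure up to each subject's tolerance limit, section 5.2 lets an uncomfortable subject stop, and section 9.4.1 ends participation after a side effect.

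**Working it through.** **1. The plan's own figure.** The synopsis gives n = 30, effect size 0.68 and power 0.95, without naming the test. A two-sided paired t-test at 0.05 (noncentral t, 29 degrees of freedom, noncentrality 0.68 × √30) has power 0.949, which matches. This basis is used below.

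**2. What leaves the test: an example.** Suppose 3 of 30 subjects stop after the fourth measurement of a day. Values collected: 27 × 6 + 3 × 4 = 174. The six-measurement test keeps 27 subjects and 162 values and drops 12 completed values. A mixed model uses all 174. On the paired-t basis, 27 subjects give power 0.925.

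**3. Expected loss over one day.** Let p be the assumed stopping risk in each of the five mobilisation intervals. The documents give no value. Complete subjects are 30(1 − p)^5. Completed values lost from the test are 30 × Σ k·p·(1 − p)^(k−1), k = 1 to 5. Power is for measurement 6 minus measurement 2, which is one reading of repetitive versus single mobilisation in section 10.1. The mixed-model column treats the covariance as known (correlation 0.5–0.9, compound symmetry or AR(1)), so it is an upper figure.

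| p | Complete subjects | Values lost | Power, completers | Power, mixed model |
|---|---|---|---|---|
| 0 | 30 | 0 | 0.949 | 0.949 |
| 1% | 28.5 | 4.4 | 0.939 | 0.942–0.943 |
| 2% | 27.1 | 8.5 | 0.926 | 0.933–0.937 |
| 5% | 23.2 | 19.7 | 0.879 | 0.901–0.913 |

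At 2% the whole loss is 0.949 − 0.926 = 0.023, of which the model recovers at most 0.007–0.011. The rest comes from not replacing drop-outs.

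**4. Covariance estimated from 30 subjects.** This was simulated for one day at p = 2%, with 4000 trials per setting, unstructured REML, and degrees of freedom equal to completers minus 1. Power for completers and for the model was 0.923/0.928 and 0.924/0.928 under compound symmetry (correlation 0.6, 0.8), and 0.928/0.937 and 0.927/0.935 under AR(1). A second run of 3000 trials gave gains of 0.007 and 0.010. The realistic gain is therefore 0.004–0.010.

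**5. Covariance choice.** In the same simulations type I error was 0.043–0.057 with an unstructured fit. With compound symmetry fitted under true AR(1) it was 0.10–0.13. If the two days' changes correlate at r = 0.3 or 0.5 and are treated as independent, size is 2 × (1 − Φ(1.96/√(1 + r))) = 0.086 or 0.110.

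**6. Bias, secondary VAS only.** Assumptions: SD 2, correlation 0.6–0.8, means rising from 3.0 to 4.2, and a stop when VAS exceeds 7.5 or 8.
- If the triggering discomfort is not recorded (5–12% stop), the 6-minus-2 change is understated by 0.03–0.17 cm in the likelihood model and by 0.01–0.11 cm in completers, a ratio of about 1.5–2.0.
- If it is recorded (4–9% stop), the likelihood bias is within 0.001 cm and the completers' bias is 0.05 cm or less.

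**The case against.** Four arguments narrow the point.

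- **Section 10.4 promises inclusion in the data analysis, not in the MANOVA.** Section 11.2.1 describes the Excel work as further analysis of the data, so partial data could be used there. This stands for description. It does not help the test, and 10.4 does not say that description is all it means.
- **Sections 7.4, 8.5 and 9.1.6 ask only for use where feasible.** This also stands. Read together, the sections are softer than 10.4 alone, but 10.4 is the statistical rule and lacks the qualifier.
- **Not every drop-out is lost.** A subject who completes day 1 and misses day 2 has all six measurements, and the named model has no day factor, so an analysis by day would use that subject's day 1 in full. The plan does not say whether days are pooled, averaged or analysed separately, which is a separate gap.
- **The effect is tiny.** Subjects are healthy adults aged 18 to 30, section 3.7 rates the risk as small, and the simulated gain comes from a one-day model. All true, which is why the point is minor.

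A reader might infer that 10.4 cannot be carried out at all, or that the named analysis discards every drop-out. The documents support neither, for the first and third reasons above. A reader might also infer that the primary result would be biased. Nothing in the documents shows that: the bias figures concern only the secondary VAS under assumed stopping rules.

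**Conclusion.** The point holds as a minor inconsistency. For subjects who stop within a session, section 10.4 includes their completed intervals, while the only named test, in its usual form, leaves those subjects out and no other analysis is named. This follows from the text and needs no assumed rate.

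Its size does depend on assumptions. It is nil if nobody stops within a session, and about 0.01 in power or less at an assumed 2% per interval. That figure rests on the paired-t reading of the stated power, the 6-minus-2 contrast and a one-day model. It was not obtained for a two-day model. A mixed model recovers only part of the loss, because drop-outs are not replaced.

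**What to change.** **Preferred.** In section 10.3.2, replace the listwise MANOVA with a likelihood-based linear mixed model (REML, SPSS MIXED) on all completed intervals of all subjects. State:

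- measurement as a fixed effect;
- an unstructured covariance over the six measurements within a day, not compound symmetry;
- a small-sample degrees-of-freedom method, for example Satterthwaite;
- whether the model is applied by day or, if both days enter one model, how the correlation between days is handled.

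Keep the section 10.2 rule for interrupted intervals, tabulate stops by interval, and report the complete-subject analysis as a sensitivity check.

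**Downside to state in the plan.** The model assumes data are missing at random. If the discomfort behind a stop falls inside an interval and goes unrecorded, its bias in the VAS change may exceed the completers' bias.

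**Alternative.** If the MANOVA is kept, reword section 10.4 to say that subjects who stop within a session are described but not tested. This alone removes the conflict.

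**Cost.** Wording in 10.3.2 and 10.4, or in 10.4 alone, with the same software and no new data. Under section 2.10 the change needs examination by, or notification to, the ethics committee and Swissmedic. With no drop-outs and an unstructured covariance, the one-day 6-minus-2 estimate and its standard error equal those of the paired analysis, so nothing is lost by the change.
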